**5. What is your plan for secondary variable analysis?**

Include the following:  
--A sketch of the analysis to assess secondary study objectives.  
--For phase III studies, the power/precision of the study to address the secondary objective(s).

**Answer/Response:** Same as above

**6. Have you been working with a statistician in designing this protocol?**

**Answer/Response:** Yes.

**IF YES, what is their name?**

**Answer/Response:** [name], University of Virginia Sr. Biostatistician

**7. Will data from multiple sites be combined during analysis?**

**Answer/Response:** No

INSTRUCTIONS: IF YES, answer the following questions

**7(a). Does the study involve randomization?**

**Answer/Response:**

**IF YES, will randomization be done at each site or among sites?**

**Answer/Response:**

**7(b). Has the sample size calculation considered the variation among sites?**

**Answer/Response:**

**7(c). When combining the data from multiple sites to assess the study results, is the effect of the treatment to be tested (or the association to be tested) assumed to be the same across sites or vary among sites? What is the modelling strategy?**

**Answer/Response:**

**7(d). Is there a common protocol used in all sites?**

**Answer/Response:**

**IF NO, how will differences among sites, such as those related to the implementation, inclusion criteria, patient characteristics, or other sites characteristics, be considered to assess the study results?**

**Answer/Response:**

## Biomedical Research

### 1. What will be done in this protocol?

#### **INSTRUCTIONS:**

This should include everything that will be done as part of this protocol. Do not repeat information that is included in other sections such as Background or Hypothesis sections. This section should include an indication of which research interventions if any offer a prospect for direct benefit and which interventions (invasive measurements, collection of blood, tissue, data, surveys, etc.) are being done solely to answer a research question and generate generalizable knowledge. If the interventions done solely for research purposes are associated with greater than minimal risk they need to be justified. Describe and justify any control and experimental arm and include method, dose, and duration of drug administration. Reference any claim of clinical equipoise if applicable.

If you are obtaining specimens or data, provide information regarding the type of specimen/data, amount of specimen needed and how the specimen/data will be obtained and what analysis will be done with the specimen/data.

Special note for studies with waiver of consent/waiver of documentation of consent:

Include a statement regarding how subjects will be recruited. For other studies this information is captured in Recruitment does not need to be duplicated in this section.

**Answer/Response:** We will use a convenience sampling scheme to identify potential study participants. Documentation of informed consent will be recorded. Electrical Impedance Tomography (Pulmovista 500; Draeger, Lubeck, Germany), which provides non-invasive and radiation free monitoring, will be used to monitor and measure regional distribution of ventilation during I.S and EzPAP® lung expansion therapy. The PulmoVista 500 EIT device has a reported high patient safety profile and poses minimal patient risk. All study procedures will take place at University of Virginia Medical Center, Second Floor, Pulmonary Diagnostics & Respiratory Therapy Services, Room 2025.

[figure not shown]
IRB-HSR # 19661: A descriptive observational pilot study comparing regional distribution of ventilation during lung expansion therapy in healthy human subjects

Procedure set-up and device calibration will occur according to Draeger provided PulmoVista 500 (Draeger; Lubeck, Germany) EIT training and operation manual:

- Study participant preparation
  - Researcher will select an electrode belt and respective patient cable sizes after measuring participant's chest circumference with paper measurement tape placed across the midclavicular line at intercostal space 4 -5. Electrode belt size will be selected according to the following chest circumference measurements:

Chest circumference	Color	Size
70 to 85 cm (28 to 33 in)	Medium blue	(S)
80 to 96 cm (31 to 38 in)	Dark blue	(M)
92 to 110 cm (36 to 43 in)	Dark red	(L)
106 to 127 cm (42 to 50 in)	Gray	(XL)
124 to 150 cm (49 to 59 in)	Violet	(XXL)

- A patient cable of the same electrode belt size will be selected and connected to the electrode belt before connection to study participants. Researchers will align and snap connect the patient cable snaps over the electrode belt studs by aligning respective snaps and studs in ascending numerical order from 1 to 16 (see below).

[figure not shown]
- A light spray of warm tap water will be applied to the electrode surface on the electrode belt before it is applied to study participants to optimize conductivity between the skin and electrodes.
- Attaching electrode belt and reference electrode to study participant while they are positioned at 45-degrees sitting in a reclining chair.
  - The electrode belt/cable combination will be attached around the thorax of each study participant at the level of the 4th – 5th intercostal space, unless mammary tissue prevents this site of application. An alternative application site will be located immediately below the mammary tissue if necessary. Left to right belt orientation will be maintained with color coded patient cable ports signifying left and right side (See image).
  - A researcher will snap the electrode belt closed after verifying proper belt position. The belt's black electrodes should have close contact with the study participant's skin at this point.

IRB-HSR # 19661: A descriptive observational pilot study comparing regional distribution of ventilation during lung expansion therapy in healthy human subjects

- An adhesive ECG electrode will be placed on the study participant's right upper abdominal quadrant and then the patient cable reference electrode snap will be attached to the ECG electrode.
- The patient cable will then be connected to the EIT monitoring device (PulmoVista 500, Lubeck, Germany) via a color coded trunk cable orientation that aligns with the patient cable left and right orientation (See image).

- EIT device calibration and signal check
  - Researcher will initiate a PulmoVista 500 EIT monitoring device calibration each day prior to performing new study participant EELI measurements.
  - A skin-electrode signal check will be performed to ensure that a minimum of 15 of 16 electrodes have sufficient contact with the participant's skin surface and signal quality is stable. Researchers will use the following status display and explanation to determine adequacy of electrode contact and signal quality.

Status	Explanation
Gray	Skin-electrode contact is sufficient for measurement to proceed
White	Skin-electrode contact is unstable, measurement will proceed but signal quality may be impaired
Red	Skin-electrode contact is insufficient for measurement to proceed

• M

**Monitoring sessions and Lung Expansion Therapy procedure**

- **Lung expansion therapies will occur as follows:**
  - Study participants will sit with their back against a reclining chair with backrest adjust to 45-degrees.
- Monitoring will be initiated after researcher performs PulmoVista 500 EIT device (Draeger; Lubeck, Germany) setup and calibration.
- Approximate monitoring/measurement duration is 15-minutes.

IRB-HSR # 19661: A descriptive observational pilot study comparing regional distribution of ventilation during lung expansion therapy in healthy human subjects

- Two study investigators will be present during Incentive Spirometry and monitoring session. One study investigator will assist with EIT interface application and provide instruct study participants on how to perform I.S. therapy properly. A second study investigator will perform EIT device set-up and monitoring only.

**INCENTIVE SPIROMETRY GROUP**

- A study investigator will instruct the study participant to strive for an inspiratory capacity volume target as determined by the I.S. device’s predicted volume nomogram table (See below).

**MALE**  
HEIGHT IN INCHES

	58"	60"	62"	64"	66"	68"	70"	72"	74"	76"	78"
20	2000	2200	2400	2600	2800	3000	3200	3400	3600	3800	4000
25	1950	2150	2350	2550	2750	2950	3150	3350	3550	3750	3950
30	1900	2100	2300	2500	2700	2900	3100	3300	3500	3700	3900
35	1800	2000	2200	2400	2600	2800	3000	3200	3400	3600	3800
40	1750	1950	2150	2350	2550	2750	2950	3150	3350	3550	3750
45	1700	1900	2100	2300	2500	2700	2900	3100	3300	3500	3700
50	1650	1850	2050	2250	2450	2650	2850	3050	3250	3450	3650
55	1550	1750	1950	2150	2350	2550	2750	2950	3150	3350	3550
60	1500	1700	1900	2100	2300	2500	2700	2900	3100	3300	3500
65	1400	1600	1800	2000	2200	2400	2600	2800	3000	3200	3400
70	1350	1550	1750	1950	2150	2350	2550	2750	2950	3150	3350
75	1300	1500	1700	1900	2100	2300	2500	2700	2900	3100	3300
80	1250	1450	1650	1850	2050	2250	2450	2650	2850	3050	3250

**FEMALE**  
HEIGHT IN INCHES

	58"	60"	62"	64"	66"	68"	70"	72"	74"
20	1900	2100	2300	2500	2700	2900	3100	3300	3500
25	1850	2050	2250	2450	2650	2850	3050	3250	3450
30	1800	2000	2200	2400	2600	2800	3000	3200	3400
35	1750	1950	2150	2350	2550	2750	2950	3150	3350
40	1700	1900	2100	2300	2500	2700	2900	3100	3300
45	1650	1850	2050	2250	2450	2650	2850	3050	3250
50	1600	1800	2000	2200	2400	2600	2800	3000	3200
55	1550	1750	1950	2150	2350	2550	2750	2950	3150
60	1500	1700	1900	2100	2300	2500	2700	2900	3100
65	1450	1650	1850	2050	2250	2450	2650	2850	3050
70	1400	1600	1800	2000	2200	2400	2600	2800	3000
75	1350	1550	1750	1950	2150	2350	2550	2750	2950
80	1300	1500	1700	1900	2100	2300	2500	2700	2900

**Incentive Spirometry procedure**

A study investigator will provide instruction on Incentive Spirometry procedure performance before supervised therapy and monitoring begins.

- Five minutes of eupneic ventilation EIT monitoring will occur before I.S. therapy commences.
- Study participants will be asked to take 10 deep breaths through the incentive spirometer’s mouthpiece, followed by a 60 second pause.
- The 10-breath cycle will be repeated three times with respiratory therapist coaching.
- Five minutes of eupneic ventilation EIT monitoring will occur following the last I.S. lung expansion therapy breath cycle.
- Incentive Spirometry therapy and monitoring session will last about 15 minutes (See image).

[figure not shown]

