**Answer/Response:**

The primary purpose of this study is to determine if there is a significant difference in regional distribution of ventilation when comparing eupneic tidal ventilation to Incentive Spirometry (I.S.) and EzPAP® lung expansion therapy in healthy adult human subjects. Electrical impedance tomography (EIT) will be used to measure regional distribution of ventilation during resting tidal ventilation and during lung expansion therapy.

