**► IF YES, describe the stratification/ randomization scheme.**

**INSTRUCTIONS:**

The stratification factors and/or the randomization plan should be identified. If there is no randomization component or important patient characteristics that will be used in treatment allocation or data analysis, a statement to this effect should be included.

Stratification factors: These are pretreatment patient characteristics which could be balanced across treatment arms by design or may be used to determine starting dose or treatment allocation.

If randomization is going to be used, the details of the randomization plan should be described.

The description should include:

- the method and timing of randomization
- the type of randomization scheme that will be used in the study
- whether or not the randomization masked/blinded/if so, then to whom is it masked/blinded
- who has access to the randomization scheme

**Answer/Response:** Parallel randomized controlled trial

A recruitment email will be sent to University of Virginia Medical Center employees who represent the target study population. A university of Virginia email distribution list will be used to mass email respiratory therapy and nursing staff working in adult ICU and surgical acute care patient wards. Word of mouth will also be used to heighten awareness about this study. Adult intensive care fellows will also be invited to participate.

The target population will be encouraged to notify a study investigator if they are interested in being screened for eligibility to participate in this study. The study PI and sub-investigators will be responsible for recruitment and enrollment.

A computer generated random numbers generator will be used to randomly assign study subjects into an I.S. or EzPAP® lung expansion therapy group after documentation of informed consent has been recorded. Randomization masking/blinding will not occur in this study. The lung expansion therapy medical device designs and their respective operational differences are impossible to conceal (See images below).

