**Answer/Response:**

The focus of this study is to use electrical impedance tomography (EIT) monitoring to determine if there is a difference in regional distribution of ventilation when comparing Incentive Spirometry (I.S.) to EzPAP® lung expansion therapy.

Baseline characteristics will be reported as:

- Sex (M/F): n (%)
- Age (years): m (SD)
- Weight (BMI): m (SD) or M (IQR) depending upon normality of data distribution
- Tobacco History: n (%); Never smoked, Current smoker; Former smoker
- Respiratory Related Comorbidities: n (%)

Baseline and post-lung expansion therapy dependent variable metrics will be reported as end-expiratory lung volume impedance (EELI) for each of the following ventilation regions of interest:

- Ventral (Level of measurement- continuous)
- Mid-ventral (Level of measurement- continuous)
- Mid-dorsal (Level of measurement- continuous)
- Dorsal (Level of measurement- continuous)

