**EzPAP® POSITIVE AIRWAY PRESSURE GROUP**

- A study investigator will provide instruction on EzPAP® procedure performance before supervised therapy and monitoring begins. A second study investigator will perform EIT device set-up and monitoring only.
- Five minutes of eupneic ventilation EIT monitoring will occur before EzPAP® therapy commences.
- Study participants will be asked to breathe normally through the EzPAP® device’s mouthpiece for 10 breaths, followed by a 60 second pause.
- The 10-breath cycle will be repeated three times with respiratory therapist coaching.
- Five minutes of eupneic ventilation EIT monitoring will occur following the last EzPAP® lung expansion therapy breath cycle.
- EzPAP® therapy and monitoring sessions will last about 15 minutes (See image).

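### Does taking the five-minute resting baseline after open allocation and device instruction bias the comparison?

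*Combined protocol and SAP*

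**What the plan says.** Under Statistical Considerations, question 1, a random number generator is used to "randomly assign study subjects into an I.S. or EzPAP® lung expansion therapy group after documentation of informed consent has been recorded", and "Randomization masking/blinding will not occur in this study". The section fixes allocation after consent but does not place it relative to the resting recording.

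The two procedure sections supply the rest of the order. In the incentive spirometry arm, "A study investigator will provide instruction on Incentive Spirometry procedure performance before supervised therapy and monitoring begins", and then "Five minutes of eupneic ventilation EIT monitoring will occur before I.S. therapy commences". In the EzPAP arm, "A study investigator will provide instruction on EzPAP® procedure performance before supervised therapy and monitoring begins", again followed by five resting minutes before therapy. Teaching on one particular device presupposes that the arm is known. The implied sequence in both arms is therefore consent, allocation, instruction, resting baseline, therapy, resting follow-up. Coaching continues during therapy: "The 10-breath cycle will be repeated three times with respiratory therapist coaching".

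The resting value has two uses. The Hypothesis section states the primary purpose as a contrast "when comparing eupneic tidal ventilation to Incentive Spirometry (I.S.) and EzPAP® lung expansion therapy". Statistical Considerations, question 2, says that "Baseline and post-lung expansion therapy dependent variable metrics will be reported as end-expiratory lung volume impedance (EELI") by region, and the monitoring section records pre/post changes in that measure.

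**The concern.** A baseline is safest when nothing about the assigned arm can have touched it. Here subjects know their arm, and just before a measurement of quiet breathing the two arms are told different things: spirometry subjects are given an inspiratory volume target and asked for deep breaths, while EzPAP subjects are asked to breathe normally. If that altered resting breathing in one arm, the between-arm difference in change from baseline would be off by the amount of the shift that had disappeared by the post-therapy reading.

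The damage would also be hard to see afterwards. With 15 per arm (assumed), a 0.05-level check of baselines has 12.5% power for a 0.3 SD shift, and chance alone produces a larger imbalance in 41% of trials. Moving the baseline ahead of allocation would make its expected between-arm difference zero by randomization, with no extra visit or recording.

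**Working it through.** **1. Which planned analyses use the baseline.**

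- Primary analysis (Statistical Considerations, question 4): between-arm t-test or Mann-Whitney test on four regional impedance values. No baseline term or change score is named.
- Abstract: one-way multivariate analysis of variance. No baseline term is named.
- Secondary research question: a reading immediately after therapy against one five minutes later. Both are post-therapy.
- Rest-versus-therapy purpose (Hypothesis section) and the recorded pre/post changes: these use the baseline, but no test is specified for them.

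A shift confined to the baseline therefore reaches none of the listed tests.

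**2. What the order does to a change score, if one were tested.** Let knowledge of the arm shift one arm's resting value by b SD, and let a fraction f of that shift remain at the post-therapy reading. The between-arm bias is then:

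| Analysis | Present order | Baseline before allocation |
|---|---|---|
| Change from baseline | −(1−f)b | +fb |
| Post-therapy value alone | +fb | +fb |

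The standardized bias on change is |bias| / √(2(1−ρ)), where ρ is the baseline-post correlation. The plan supplies the two-sided alpha of 0.0125 and the total of 30 subjects. The assumptions are 15 per arm, ρ from 0.5 to 0.8, and no device effect. The rejection rate comes from the noncentral t distribution with 28 degrees of freedom and noncentrality d√(15/2).

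For b = 0.3 and f = 0 in the present order:

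- ρ = 0.5: d = 0.3/√1.0 = 0.30, rate 4.3%.
- ρ = 0.8: d = 0.3/√0.4 = 0.47, rate 10.2%.

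The full set of change-score rates, against a nominal 1.25%:

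| b (SD) | f | Present order | Baseline before allocation |
|---|---|---|---|
| 0.1 | 0 | 1.6%–2.0% | 1.25% |
| 0.1 | 1 | 1.25% | 1.6%–2.0% |
| 0.2 | 0 | 2.5%–4.7% | 1.25% |
| 0.2 | 1 | 1.25% | 2.5%–4.7% |
| 0.3 | 0 | 4.3%–10.2% | 1.25% |
| 0.3 | 0.5 | 1.9%–3.1% | 1.9%–3.1% |
| 0.3 | 1 | 1.25% | 4.3%–10.2% |

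The columns mirror each other around f = 0.5. Below one half the earlier baseline gives the smaller error; above one half the present order does. Nothing in the documents locates f, or shows that b differs from zero. The post-only comparison has the same bias in either order.

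**3. What the other order would add.** Device teaching and handling would fall between the baseline and therapy, with the belt on. The monitoring section describes relative impedance changes, and the electrodes are moistened with a light water spray, so this interval may not be neutral. Its content would also differ by arm: a volume target in one, normal breathing in the other.

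- A differential drift of 0.2 SD over the interval would, by the same formula, give the 2.5% to 4.7% shown for b = 0.2.
- Non-differential drift with an SD of 0.2 (assumed) would multiply the standard error of the change by √((2(1−ρ)+0.04)/(2(1−ρ))). That is √1.04 = 1.02 at ρ = 0.5 and √(0.44/0.40) = 1.05 at ρ = 0.8.

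**4. Session time.** Ten resting minutes, two or three one-minute pauses, and 30 breaths at an assumed 10 to 20 per minute give 10 + 2 + 1.5 = 13.5 to 10 + 3 + 3 = 16.0 minutes, which agrees with the stated 15 or so. One to two minutes of teaching (assumed) inside the session would make it 14.5 to 18.0.

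**The case for a change.** The strongest argument for moving the baseline does not rest on error rates. A baseline taken before allocation is independent of arm by randomization, whatever b and f are, and the change and post-only analyses then carry the same bias, fb, instead of differing by the whole of b. The plan permits the move, since allocation need only follow consent. It already hides the EIT screen during therapy to limit performance bias, and it does not say how the baseline enters the analysis, so a change score cannot be excluded.

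The independence and the agreement between the two analyses are both real. The agreement, however, comes from counting any lasting effect of instruction as part of therapy. The present order gives instruction before both the resting and the therapy recordings, so in the rest-versus-therapy contrast a persisting effect of instruction cancels and what remains is closer to the effect of breathing on the device. These are two different quantities, and a statistician could reasonably want either. The screen-hiding provision concerns the therapy session and does not bear on when the baseline is taken. The silence on how baseline is used is a separate matter, which reordering the visit would not resolve.

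The mechanism is also weaker here than in a naive population. Recruitment is aimed at respiratory therapists, ICU and surgical ward nurses and intensive care fellows, at a centre where both therapies are standard practice. Many subjects will probably know the devices already, and no practice breaths before the baseline are described.

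**Conclusion.** The observation about order is a fair reading: the resting baseline is pre-therapy but follows open allocation and device-specific instruction. It is not a defect. Both arms follow the same sequence, none of the tests the plan lists is touched by a baseline-only shift, and the documents show no such shift. For an unplanned change-score test, an assumed shift of 0.1 to 0.3 SD gives a per-region error between 1.25% and 10.2% in either order, depending only on how much of the shift persists. The alternative order also adds an arm-specific interval between baseline and therapy whose effect on the signal is unknown. These figures assume 15 per arm and correlations of 0.5 to 0.8. The choice of order is a trade-off with no demonstrated net gain either way, in a proof-of-concept study of 30 healthy adults.

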**EzPAP® POSITIVE AIRWAY PRESSURE GROUP**

- A study investigator will provide instruction on EzPAP® procedure performance before supervised therapy and monitoring begins. A second study investigator will perform EIT device set-up and monitoring only.
- Five minutes of eupneic ventilation EIT monitoring will occur before EzPAP® therapy commences.
- Study participants will be asked to breathe normally through the EzPAP® device’s mouthpiece for 10 breaths, followed by a 60 second pause.
- The 10-breath cycle will be repeated three times with respiratory therapist coaching.
- Five minutes of eupneic ventilation EIT monitoring will occur following the last EzPAP® lung expansion therapy breath cycle.
- EzPAP® therapy and monitoring sessions will last about 15 minutes (See image).

